Study Title: One In Seven Gestational Diabetes Study
Sponsor: Prenome
Protocol Number: PRE001/OM001
IRB Submission Number: Pro00049373
Principal Investigator: [name]
Email: [contact]
[contact]
Address: [name]

GESTATIONAL DIABETES GENETIC AND SOCIOECONOMIC RISK PROTOCOL

VERSION DATE: 05/05/2021

STUDY SUMMARY

Investigational Agent(s) (Drugs or Devices)	N/A
IND / IDE / HDE #	No
Special Population(s)	Pregnant Women
Sample Size	10,000 Participants
Funding Source	Prenome (Industry)
Indicate the type of consent to be obtained	Electronic Consent Written Consent
Site	[name]
Research Related Radiation Exposure	Yes No 
DSMB / DMC / IDMC	Yes  No

OBJECTIVES

The objective of the **Gestational Diabetes Genetic Socioeconomic Risk Study** is to generate genome wide association study data (GWAS) to calculate polygenic risk scores (PRS) for the development of gestational diabetes in pregnant women. Prenome's GWAS study will be conducted by collecting DNA samples alongside medical and socioeconomic data and applying data science methodology to generate a polygenic risk score algorithm for gestational diabetes. Our hypothesis is that key genetic variants linked to gestational diabetes will be identified, and sociodemographic characteristics may impact epigenetic factors which further contribute to this risk of gestational diabetes. The PRS generated through our study will be combined with an analysis of epigenetic factors to produce a new method for predicting risk of developing gestational diabetes during pregnancy.

BACKGROUND

Gestational diabetes is a condition where high blood glucose levels occur during pregnancy and the mother was not diabetic before pregnancy. Between 6-9% of pregnancies are affected by this disorder. Gestational diabetes is usually diagnosed with a glucose challenge test where a blood glucose level of 190mg/dL or above would be indicative of gestational diabetes. This test usually occurs around 24-28 weeks into pregnancy. If a patient has other risk factors such as obesity or family history of diabetes, the assessment may be performed earlier.

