The end point of this study is the generation of a polygenic risk score for gestational diabetes from whole genome sequencing of 10,000 DNA samples and sociodemographic data from currently pregnant or recently (< 1 year since birth) pregnant participants.

[figure not shown]
STUDY INTERVENTION

This study does not require any intervention procedures. Participants will be recruited for saliva samples for DNA isolation and data collection only.

PROCEDURES INVOLVED

In order to generate a polygenic risk score for gestational diabetes, Prenome will conduct a GWAS by gathering DNA samples and information from 10,000

Study Title: One In Seven Gestational Diabetes Study
Sponsor: Prenome
Protocol Number: PRE001/OM001
IRB Submission Number: Pro00049373
Principal Investigator: [name]
Email: [contact]
[contact]
Address: [name]

participants who satisfy one of the following qualifications: women who are currently > 24 weeks pregnant, women who have been pregnant within the last year, women with or without a history of gestational diabetes, and women who currently have gestational diabetes.

Participants will be recruited through OB/GYN clinics, patient recruitment organizations or directly by Prenome through an established waitlist and an online advertising campaign. Interested persons will receive materials fully explaining the study and consent processes in detail through a series of pre-prepared email templates. This will include a video, a detailed description in the consent form, and information displayed on the company or study websites (www.prenome.com or www.gestationaldiabetestudy.com). All interested persons will have the option to consult Prenome staff about this study by contacting the [contact] email. This information will be presented online and in communication emails. Prenome will be accessing participant's personal information through medical records to collect information on impactful risk factors and pregnancy outcome data. Samples will be collected from two participant cohorts: a control group containing 5000 participants with normoglycemic pregnancies and a second group containing 5000 diagnosed with gestational diabetes.

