The control cohort will include 5000 adult women who are over 24 weeks pregnant or have given birth to a child within 1 year, who have not received a diagnosis of gestational diabetes and were not diabetic during or before their pregnancy. The diabetic cohort will include 5000 adult women who are over 24 weeks pregnant or have given birth to a child within 1 year, who received any diagnosis of gestational diabetes during their pregnancy. There is no adult age, race or ethnicity exclusion criteria for this study, as our intention is to generate PRS based on diverse populations in line with percentage diversity of the US population. However, minors are not eligible to participate in this study. Male participation is excluded from this

Study Title: One In Seven Gestational Diabetes Study
Sponsor: Prenome
Protocol Number: PRE001/OM001
IRB Submission Number: Pro00049373
Principal Investigator: [name]
Email: [contact]
[contact]
Address: [name]

study. Non-english speakers are excluded from recruitment, this is due to the consent process being available in English only.

VULNERABLE POPULATIONS

Vulnerable populations include pregnant women, visually impaired participants, and women with a history of gestational diabetes. No conversations or documentation given to participants will discuss pregnancy termination. Information produced in this study will be returned to participants, and will not be used to influence decisions related to termination of pregnancy. No inducements, monetary or otherwise will be offered to influence pregnancy termination. In order to ensure the safety and comfort of these participants, the collection kit aims to be as minimally invasive as possible and available to participants in their homes to reduce Covid-19 exposure in clinical environments. Visually impaired persons will have access to this study, and the instructions will be available in a verbal format to increase understanding.

RECRUITMENT METHODS

Participants will be recruited through two channels. The first is through partnered clinical sites referred to Prenome by healthcare providers, where participants receive obstetric care. Clinicians at these sites will be able to identify qualifying participants and register them through the company or study websites (www.prenome.com or www.gestationaldiabetesstudy.com) which are connected to a HIPAA compliant CRM portal, and initiate their study involvement.

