Participants will also be able to directly sign up to this study through a clinical study sign up form featured on the Prenome or study websites (www.prenome.com or www.gestationaldiabetesstudy.com). Any person currently over 24 weeks pregnant or previously pregnant within the last year may register interest in participation on the Prenome website. Prenome will use a series of standardized email templates to communicate with participants at every stage of the study including sign up, consent and kit collection. Interested persons will have access to a video and written materials explaining the study

Study Title: One In Seven Gestational Diabetes Study
Sponsor: Prenome
Protocol Number: PRE001/OM001
IRB Submission Number: Pro00049373
Principal Investigator: [name]
Email: [contact]
[contact]
Address: [name]

and consent processes in detail. They will then be able to complete the sign-up and consent process online. Participants may request a consultation with Prenome to discuss the study if they require more information. Information about study participation through this route will be advertised online including social media and pregnancy related blogs. External sites will be given access to the same advertising materials for recruitment.

COMPENSATION FOR PARTICIPATION IN RESEARCH ACTIVITIES

All participants will receive a \$20 Uber Eats or Amazon gift card, upon delivery of their saliva sample to the Prenome lead site, for contributing to this research study. The gift card will be emailed to participants by default, but participants may request a physical gift card be mailed to them.

WITHDRAWAL OF PARTICIPANTS

Participants may withdraw from the study at any stage of the process. In order to formally withdraw, participants can request a withdrawal form through the Prenome contact email ([contact]) supplied in their communication emails, consent form, collection kit or on the Prenome website. Participants can physically or digitally sign the withdrawal form, and return this to the contact email address or Prenomes mailing address. Upon receiving the withdrawal request, all sequencing, medical and sociodemographic data tied to the participant ID will be removed from the Prenome database and CRM. All saliva, DNA and library samples tied to that participant will be removed from storage and destroyed immediately.

RISKS TO PARTICIPANTS

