Once data has passed quality control, the reads generated will be aligned to reference genomes, using illumina's basespace platform to produce BAM files containing aligned reads which can be linked to the index barcodes for each participant. The participant data will be linked to the sequencing data using the individual barcode assigned at sample collection. This data will not contain names or full addresses of participants but will contain medical information and sociodemographic survey information. We will combine the study sequencing data with public genetic datasets (UKBioBank, BioBank Japan) which contain information on pregnant women. This information will be analysed for specific alleles and gene variants that can be linked to gestational diabetes using Python to identify GWAS data. The GWAS data will then be run through a variety of PRS algorithms using Python for Prenome's proprietary algorithm and Allelica for publicly available PRS algorithms.

Study Title: One In Seven Gestational Diabetes Study
Sponsor: Prenome
Protocol Number: PRE001/OM001
IRB Submission Number: Pro00049373
Principal Investigator: [name]
Email: [contact]
[contact]
Address: [name]

DATA MANAGEMENT AND CONFIDENTIALITY

All sequencing data from participant samples will be generated on the NovaSeq 6000. Sequenced data will be transferred from sequencing equipment to password protected cloud storage. This information will be anonymised and catalogued using unique identifiers to protect confidentiality. Genome sequencing data will be checked for quality control management, and then reads will be filtered and aligned to a reference genome.

These aligned reads will be matched to participant medical records, used to generate GWAS data and identify linkage of associated alleles or gene variants which can be correlated with gestational diabetes. This data may be combined with publicly available whole genome sequencing data such as the UKBiobank and Biobank Japan. Once variants have been detected, polygenic risk scores will be generated using publically available algorithms and Prenome's internal algorithms. These scores will be tied to sociodemographic risk factors, generated from the study questionnaire, to calculate a complete risk score composed of genetic and epigenetic factors. All data outcomes and statistical analyses produced by this study will be reviewed by a data monitoring committee (DMC).

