Prenome's **One in Seven Gestational Diabetes Risk Study** will involve the collection of PHI and HIPAA protected information. Specifically, Prenome will be collecting the participant's age, geographic location in the form of a zip code, and medical record numbers used in this study. Further, pregnancy related outcomes and health data will be extracted from participant medical records or gathered through the sociodemographic questionnaire. No participant names, detailed addresses or unauthorized information will be used for data analysis in this study. Participants will sign a HIPAA and PHI authorization form as part of the consent for this study. No unauthorized personnel will have access to this information, and this information will be accessible only on Prenome devices.

QUALIFICATIONS TO CONDUCT RESEARCH AND RESOURCES AVAILABLE

10,000 participants will be recruited across partner sites, online advertising and waitlist registrations. Currently, Prenome has over a thousand women who have expressed an interest in participating in this study and will undergo recruitment upon IRB approval. Prenome's established waitlist has been accrued from direct recruitment and women expressing interest through our website sign up portal.

Study Title: One In Seven Gestational Diabetes Study
Sponsor: Prenome
Protocol Number: PRE001/OM001
IRB Submission Number: Pro00049373
Principal Investigator: [name]
Email: [contact]
[contact]
Address: [name]

The study will have a dedicated team of researchers for a minimum of 1 year. This will include the Principal Investigator, NGS Scientist, Research Associate, Data Scientist and a Recruitment Coordinator. Prenome has access to the appropriate laboratory space, sequencing equipment, reagents and storage facilities to complete the research study. All employees involved will be required to follow SOPs to conduct research protocols.

MULTI-SITE RESEARCH

Participants will be recruited at multiple external sites for this study. All sites will be required to sign a IRB authorization agreement, and must follow the protocols for recruitment outlined by Prenome. Sites will identify and register qualifying participants, and register them using a secured CRM. All external sites will be provided with the advertising materials created by Prenome for social media based advertising.

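### The protocol does not fix whether case or control status comes from the medical record or from a questionnaire that may be answered before the glucose test

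*Protocol*

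**What the plan says.** Four places in the protocol bear on where the outcome comes from.

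- **Procedures Involved:** "Prenome will be accessing participant's personal information through medical records to collect information on impactful risk factors and pregnancy outcome data". The same section sets the design as "a control group containing 5000 participants with normoglycemic pregnancies and a second group containing 5000 diagnosed with gestational diabetes".
- **Data Management and Confidentiality:** "These aligned reads will be matched to participant medical records, used to generate GWAS data". The questionnaire appears there as the source of sociodemographic risk factors.
- **Protected Health Information:** "pregnancy related outcomes and health data will be extracted from participant medical records or gathered through the sociodemographic questionnaire". Nothing says which source prevails, or what happens if they disagree.
- **Inclusion and Exclusion Criteria:** cases are women "who received any diagnosis of gestational diabetes during their pregnancy" and controls are women "who have not received a diagnosis of gestational diabetes and were not diabetic during or before their pregnancy". No source is named for either, and no glucose result is required of controls.

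Three further statements matter:

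- Under Recruitment Methods, clinicians identify eligible women at partner sites, but there is a second route: "Participants will also be able to directly sign up to this study through a clinical study sign up form".
- The questionnaire covers medical history and becomes available when the kit is registered (Procedures Involved). No repeat questionnaire is described.
- The Background places the usual diagnostic test at around 24-28 weeks, while women qualify once they are over 24 weeks pregnant.

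**The concern.** Case or control status is the one outcome of the association study, and the risk score that forms the study endpoint is built on it. As written, a woman's status could rest on the record or on her own answer, and different women could be classified by different rules.

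Timing makes this more than loose wording. A woman who registers her kit at 25 weeks can correctly state that she has no diagnosis, be tested two weeks later and be diagnosed. A record read afterwards would place her among the cases; the questionnaire would leave her among the controls. The section on sharing results treats pregnancy outcomes as already defined, which need not be true of her. The criterion of no diagnosis received is also weaker than the normoglycemic control group promised under Procedures Involved.

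At stake are power and the accuracy of the estimated weights. If false cases and false controls enter independently of genotype, true allele-frequency differences shrink and the score built from them loses accuracy.

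**Working it through.** **The plan's own figure.** The Study Summary gives "10,000 Participants", which agrees with 5,000 + 5,000. No significance level, power, effect size or allele frequency is stated, so there is no power calculation to reproduce. What follows is an illustration under assumptions.

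**Inputs.** From the protocol: 5,000 women per group, hence 10,000 alleles per group. Assumed: two-sided level 5e-8 (z = 5.45), control allele frequency 0.30, true allelic odds ratio 1.21 or 1.30, and error rates of 2% to 10%.

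**Attenuation.** Let *a* be the share of labelled cases who are unaffected and *b* the share of labelled controls who have gestational diabetes, independent of genotype. The observed allele-frequency difference is (1 − a − b) times the true one. Information is kept in proportion to (1 − a − b)², so the same power needs about 5,000/(1 − a − b)² per group. If only a share *f* of each group is self-reported and records are taken as correct, the factor is 1 − f(a + b).

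**Power.** With difference d, power = Φ[(d − 5.45·se₀)/se₁], where se₀ is the pooled and se₁ the unpooled standard error. For odds ratio 1.21, the case odds are (0.30/0.70) × 1.21 = 0.519, so the case frequency is 0.3415 and d = 0.0415. At 5%/5% this becomes 0.0415 × 0.90 = 0.0373.

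| Self-reported share | a / b | Factor | Per group for equal power | Power, OR 1.21 | Power, OR 1.30 |
|---|---|---|---|---|---|
| none | 0 / 0 | 1.00 | 5,000 | 80% | 99.9% |
| half | 5% / 5% | 0.95 | about 5,540 | 70% | 99.8% |
| all | 2% / 2% | 0.96 | about 5,425 | 72% | 99.8% |
| all | 5% / 5% | 0.90 | about 6,173 | 58% | 99.1% |
| all | 10% / 10% | 0.80 | about 7,812 | 34% | 93% |

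With all status self-reported, the observed odds ratio for a true 1.21 is 1.20, 1.19 and 1.16 at 2%, 5% and 10% error on each side.

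**A bound on false controls.** The Background puts gestational diabetes at 6-9% of pregnancies. If the women who volunteer are not enriched for the condition, controls with no screening at all would give b of about 0.06 to 0.09. With a = 0 the factor is then 0.94 to 0.91. The 10%/10% row therefore goes beyond what the timing gap alone could produce.

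**Cost of exclusion.** With error e on each side, keeping self-report-only women retains (1 − 2ef)² of the information. Dropping them without replacement retains 1 − f.

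- f = 0.5, e = 5%: (1 − 0.05)² = 0.90 against 0.50.
- f = 0.2, e = 10%: (1 − 0.04)² = 0.92 against 0.80.

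**The case against.** The strongest reply is that the sentence with the word *or* sits in a privacy section that lists what information is collected. It can be read as some items from records and others from the questionnaire. The procedural and analysis sections both point to records. Medical record numbers are collected and a HIPAA authorization is signed as part of consent, with no exception for women who sign up online. This stands to the extent that a reader might infer the protocol assigns cohorts by self-report, and it does not say that. It leaves the source open, and no section requires that status be confirmed from the record.

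The reply is also right about size. The larger losses apply assumed errors to all 10,000 women and use an effect at which power is about 80%, where it is most sensitive. They also treat records as error-free, which is itself an assumption.

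Four further inferences are tempting and are not supported:

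- **Every genetic effect is diluted.** Only variants that are truly associated are attenuated; null variants are unaffected.
- **Accuracy differs by recruitment channel and so biases the score.** The protocol gives no accuracy or ancestry data by channel, and online entry does not imply self-reported status.
- **The gift card invites misreporting.** Cases and controls receive the same amount, so it gives no reason to misstate status.
- **Women with self-report only should be left out of the primary analysis.** In the examples worked above, exclusion loses more information than the errors do.

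Finally, it can be said that asking for a glucose result tightens the control definition, and that sensitivity analyses belong in a statistical analysis plan. The first is true of the inclusion criteria, but it matches the normoglycemic group stated under Procedures Involved. On the second, the source of the label is a data-collection rule: an analysis plan cannot recover records that were never read or were read too early.

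**Conclusion.** The point holds as an inconsistency in how the study's only outcome is sourced, joined to a timing gap that lets a truthful questionnaire answer misclassify a control. Both can be read directly from the protocol and need no assumed figure.

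The consequence is assumption-dependent. With errors independent of genotype, the loss runs from slight (factor 0.96 at 2%/2%, or power still about 99% for an odds ratio of 1.30 at 5%/5%) to material (power 58% instead of 80% for 1.21 at 5%/5%, if all status were self-reported). If records supply most statuses, as two sections suggest, the loss is nearer the slight end. The protocol gives neither the error rates nor the self-reported share, so no single figure can be defended. This is a worthwhile and inexpensive correction; it does not show that the design fails.

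**What to change.** Reconcile Procedures Involved, Inclusion and Exclusion Criteria, Data Management and Confidentiality, and Protected Health Information so that they state one rule:

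- Case or control status is taken from the medical record of the qualifying pregnancy, read after the glucose test result is available: a recorded diagnosis for cases, a recorded non-diabetic result for controls.
- Questionnaire status is used only as a flagged fallback when no record can be obtained.
- The source of status is logged for each participant.
- A sensitivity analysis is limited to women with record-confirmed status. Women with self-report only stay in the primary analysis by default.

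The cost is a wording change, some extra record abstraction, and later confirmation for women enrolled before they are tested. Record access, record numbers and the HIPAA authorization are already planned.
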